5.4 APPENDIX 4 DATA HANDLING CONVENTIONS

Demographic formulas

Age of onset of CSU is calculated as:

$$\text{Year of CSU diagnosis} - \text{Year of birth}$$

BMI is calculated as:

$$\text{Weight in kg} / (\text{height}^2 \text{ in meters})$$

Renal function formulas

For adults, creatinine clearance (CLcr) value will be derived using the equation of Cockcroft and Gault:

$$\text{CLcr (ml/min)} = \frac{(140 - \text{age}) \times \text{weight (kg)} \times (1 - 0.15 \times \text{sex (0-M, 1-F)})}{(0.814 \times \text{creatinine (\mu mol/L)})}$$

For participants <18 years old, CLcr value will be derived using the equation of GFR Bedside Schwartz

$$\text{GFR (mL/min/1.73 m}^2\text{)} = \text{k} \times \text{height (cm)} / \text{sCr (mg/dL)}$$

where the coefficient k = 0.55 for children <12; k = 0.65 for male adolescent participants or k = 0.55 for female adolescent participants

CLcr will be calculated using the last weight measurement on or before the visit of the creatinine measurement and age at the lab sampling day. Here age is calculated as following:

$$\text{Age} = \text{age collected at screening} + \text{integer part of (lab sampling analysis day / 365.25)}$$

Data handling conventions for other secondary endpoints

For the UCT, in case of missing items the score for that participant will be left missing.

- i. For the DLQI, handing of missing items is as follows: If one question is left unanswered this is scored 0 and the scores are summed and expressed as usual out of a maximum of 30,
- ii. If two or more questions are left unanswered, the questionnaire is not scored,
- iii. If question 7 is answered 'yes', this is scored 3 even if in the same question one of the other boxes is ticked,
- iv. If question 7 is answered 'no' or 'not relevant' but then either 'a lot' or 'a little' is ticked, this is scored 2 or 1,
- v. If two or more response options are ticked for one question, the response option with the highest score should be recorded.

For the CDLQI, handling of missing items is as follows:

- i. If one question is left unanswered, this is scored 0 and the scores are summed and expressed as usual out of a maximum of 30,
- ii. If two or more questions are left unanswered, the questionnaire is not scored,
- iii. If two or more response options are ticked for one question, the response option with the highest score should be recorded.

For the CU-Q2oL total score, the raw total score will be converted to a 0 to 100 score for analysis using the following formula:

$$\text{CU-Q2oL total score} = (\text{raw score} - 23) * 100 / 92$$

Daily e-diary weekly scores

For the daily efficacy endpoints (ISS, UAS, HSS, and AAS), the time period used to calculate the weekly score at each designated study day is summarized in [Table 9](#). Randomization day is used as the reference day (Day 1).

Table 9 - Weekly efficacy assessments from daily e-diary

| Analysis visit | Day range for calculating weekly score | Target day |
|----------------|--|------------|
| Week 1 | 2-8 | 8 |
| Week 2 | 9-15 | 15 |
| Week 3 | 16-22 | 22 |
| Week 4 | 23-29 | 29 |
| Week 5 | 30-36 | 36 |
| Week 6 | 37-43 | 43 |
| Week 7 | 44-50 | 50 |
| Week 8 | 51-57 | 57 |
| Week 9 | 58-64 | 64 |
| Week 10 | 65-71 | 71 |
| Week 11 | 72-78 | 78 |
| Week 12 | 79-85 | 85 |
| Week 13 | 86-92 | 92 |
| Week 14 | 93-99 | 99 |
| Week 15 | 100-106 | 106 |
| Week 16 | 107-113 | 113 |
| Week 17 | 114-120 | 120 |
| Week 18 | 121-127 | 127 |
| Week 19 | 128-134 | 134 |
| Week 20 | 135-141 | 141 |
| Week 21 | 142-148 | 148 |
| Week 22 | 149-155 | 155 |
| Week 23 | 156-162 | 162 |
| Week 24 | 163-169 | 169 |
| Week 25 | 170-176 | 176 |
| Week 26 | 177-183 | 183 |
| Week 27 | 184-190 | 190 |
| Week 28 | 191-197 | 197 |
| Week 29 | 198-204 | 204 |
| Week 30 | 205-211 | 211 |
| Week 31 | 212-218 | 218 |
| Week 32 | 219-225 | 225 |
| Week 33 | 226-232 | 232 |
| Week 34 | 233-239 | 239 |
| Week 35 | 240-246 | 246 |
| Week 36 | 247-253 | 253 |

Analysis windows for time points

For the safety assessment, the reference date for the derivation of relative days of events or findings will be the date of first IMP administration. Selected safety variables will be summarized by the analysis window defined in [Table 10](#) for the by visit descriptive analysis. All available values from central lab will be assigned to the appropriate visit window. In the event of multiple measurements of the same test in the same window, the one closest to the targeted visit date will be used for the by-visit summary. If they are at the same number of days away from the target day, the latest one will be used. For procedures planned on Visit 2, if it is done on the same date as the first IMP injection but the performance time is missing, it will belong to Visit 2 time window.

Table 10 - Time window for safety endpoints

| Visit | Target Day | Time windows for | | | | | | |
|----------------------|------------|------------------|--------------------------------------|-------------------------|-----------------|-----------------|---------------|--------|
| | | Vital signs | Hematology, biochemistry, urinalysis | Hepatitis, HIV serology | Serum pregnancy | Urine pregnancy | Physical exam | ECG |
| Visit 1 | -28 to -14 | <-14 | <-14 | 1- | <-14 | | <-14 | 1- |
| Visit 2 (Week 0) | 1 | -14-1- | -14-1- | | | -14-1- | | -14-1- |
| Week 4 | 29 | | | | | 1+-42 | | |
| Week 8 | 57 | | | | | 43-70 | | |
| Visit 3 (Week 12) | 85 | 1+-126 | 1+-126 | | | 71-98 | | |
| Week 16 | 113 | | | | | 99-126 | | |
| Week 20 | 141 | | | | | 127-154 | | |
| Visit 4 (Week 24) | 169 | 127-210 | 127-210 | | | 155-182 | 1+-210 | 1+ |
| Week 28 | 197 | | | | | 183-210 | | |
| Week 32 | 225 | | | | | 211-238 | | |
| Visit 5 (Week 36) | 253 | >210 | >210 | | | >238 | >210 | |

1-: up to 1st dose date/time; 1+: after 1st dose date/time;

For the efficacy assessment, the reference date for the derivation of relative days of events or findings will be the randomization day. If a participant receives IMP prior to the randomization by mistake, the reference date of efficacy assessment will be the date of the first IMP administration for that participant. For the primary analyses, all available values of scheduled measurements will be assigned to the appropriate visit window according to [Table 11](#). In the event of multiple measurements of the same test in the same window, the one closest to the targeted visit date will be used for the by-visit summary. If they are at the same number of days away from the target day, the latest one will be used.

Table 11 - Time window for efficacy variables

| Visit | Target Day | Time windows for | | |
|-------------------|------------|--------------------------|--------|---------|
| | | UCT, DLQI/CDLQI, CU-Q2oL | PGIC | PGIS |
| Visit 1 | -28 to -14 | | | <-14 |
| Visit 2 (Week 0) | 1 | <1- | | -14-1- |
| Visit 3 (Week 12) | 85 | 1+-126 | 1+-126 | 1+-126 |
| Visit 4 (Week 24) | 169 | 127-210 | >126 | 127-210 |
| Visit 5 (Week 36) | 253 | >210 | | >210 |

1-: up to randomization and before 1st dose date/time; 1+: after randomization or 1st dose date/time

For the pharmacokinetics/pharmacodynamics variables summary, the reference date for the derivation of relative days of measurements will be the date of first IMP administration if the participant is treated with study intervention, or the randomization date if the participant is not treated. Pharmacokinetics /pharmacodynamics variables will be summarized by the analysis window defined in [Table 12](#) for the by visit descriptive analyses. All available values of measurements will be assigned to the appropriate visit window. In the event of multiple measurements of the same test in the same window, the one closest to the targeted visit date will be used for the by-visit summary. If they are at the same number of days away from the target day, the latest one will be used. For procedures planned on Visit 2, if it is done on the same date as the first IMP injection but the performance time is missing, it will belong to Visit 2 time window.

Table 12 - Time window for pharmacokinetics/pharmacodynamics variables

| Visit | Target Day | Serum dupilumab, ADA, Total IgE | Skin biopsy (substudy) | Basophil activation (substudy) |
|-------------------|------------|---------------------------------|------------------------|--------------------------------|
| Visit 1 | -28 to -14 | | | |
| Visit 2 (Week 0) | 1 | <1- | <1- | <1- |
| Visit 3 (Week 12) | 85 | 1+-126 | | 1+-126 |
| Visit 4 (Week 24) | 169 | 127-210 | >1+ | >126 |
| Visit 5 (Week 36) | 253 | >210 | | |

1-: up to 1st dose date/time or randomization if participant is not treated; 1+: after 1st dose date/time or randomization date if participant is not treated;

Unscheduled visits

Unscheduled visit measurements of laboratory data, vital signs and ECG will be used for computation of baseline, the last on-treatment value, analysis according to PCSAs, and the shift summaries for safety. They will also be included in the by-visit summaries if they are re-allocated to scheduled visits. Unscheduled visit measurements for efficacy data will be included in the by-visit summaries if they are re-allocated to scheduled visits.

5.5 APPENDIX 5 SAMPLE SAS CODE

The multiple imputation and analysis model for the primary analysis approach will be built with the following sample SAS code.

1. 40 datasets with a monotone missing pattern will be obtained, induced by Markov Chain Monte Carlo (MCMC) method on participants who have not taken selected prohibited medications and/or rescue medications or have not discontinued study intervention due to lack of efficacy prior to Week 24.

A large rectangular area of the page is completely blacked out, representing a redaction of the SAS code for the first step.

2. For each of the imputed dataset with monotone missing pattern in step 1, the remaining missing data will be imputed using the regression method for the monotone pattern with adjustment for covariates including intervention groups, region, angioedema status at baseline and baseline value of the response variable.

[figure not shown]
A large rectangular area of the page is completely blacked out, representing a redaction of the SAS code for the second step.

3. Each of the 40 imputed datasets will be merged with the one dataset imputed by WOCF approach, and then be analyzed using the main statistical model. These 40 imputed datasets will be saved.

A large rectangular area of the page is completely blacked out, representing a redaction of the SAS code for the third step.

4. Applying Rubin's rule to combine analysis results (point estimates and standard errors) from 40 imputations using PROC MIANALYZE for the LS means and difference in LS means between dupilumab and placebo. Sample code:

5.6 APPENDIX 6 SELECTION CRITERIA FOR AE/MEDICATION GROUPINGS

Table 13 - List of PTs or Medications for CMQs/CDGs

| Grouping | Preferred Term/ Medication Code | Preferred Term/ Medication |
|----------------|------------------------------------|--|
| Conjunctivitis | 1001257 | Adenoviral conjunctivitis |
| Conjunctivitis | 10010725 | Conjunctival irritation |
| Conjunctivitis | 10010726 | Conjunctival oedema |
| Conjunctivitis | 10010736 | Conjunctival ulcer |
| Conjunctivitis | 10010741 | Conjunctivitis |
| Conjunctivitis | 10010744 | Conjunctivitis allergic |
| Conjunctivitis | 10010745 | Conjunctivitis chlamydial |
| Conjunctivitis | 10010749 | Conjunctivitis gonococcal neonatal |
| Conjunctivitis | 10010754 | Conjunctivitis tuberculous |
| Conjunctivitis | 10010755 | Conjunctivitis viral |
| Conjunctivitis | 10018258 | Giant papillary conjunctivitis |
| Conjunctivitis | 10021629 | Inclusion conjunctivitis |
| Conjunctivitis | 10030861 | Ophthalmia neonatorum |
| Conjunctivitis | 10048908 | Seasonal allergy |
| Conjunctivitis | 10049458 | Herpes simplex virus conjunctivitis neonatal |

| Grouping | Preferred Term/ Medication Code | Preferred Term/ Medication |
|------------------------------------|------------------------------------|-----------------------------------|
| Conjunctivitis | 10051625 | Conjunctival hyperaemia |
| Conjunctivitis | 10053991 | Inclusion conjunctivitis neonatal |
| Conjunctivitis | 10061784 | Conjunctivitis bacterial |
| Conjunctivitis | 10062889 | Pingueculitis |
| Conjunctivitis | 10063669 | Photoelectric conjunctivitis |
| Conjunctivitis | 10067317 | Oculorespiratory syndrome |
| Conjunctivitis | 10067817 | Acute haemorrhagic conjunctivitis |
| Conjunctivitis | 10069166 | Blebitis |
| Conjunctivitis | 10071570 | Ligneous conjunctivitis |
| Conjunctivitis | 10074701 | Noninfective conjunctivitis |
| Conjunctivitis | 10075264 | Oculoglandular syndrome |
| Conjunctivitis | 10080825 | Conjunctivitis fungal |
| Conjunctivitis | 10084034 | Conjunctival suffusion |
| Intravenous immunoglobulin therapy | CAS 8000012671 | IMMUNOGLOBULIN HUMAN NORMAL |
| Intravenous immunoglobulin therapy | CAS 8000050682 | IMMUNOGLOBULIN, PORCINE |
| Intravenous immunoglobulin therapy | CAS 8000056919 | IMMUNOGLOBULIN G HUMAN |
| Intravenous immunoglobulin therapy | CAS 8600000563 | IMMUNOGLOBULINS NOS |
| Intravenous immunoglobulin therapy | CAS 8600001670 | IMMUNOGLOBULIN HUMAN NORMAL SLRA |
| Intravenous immunoglobulin therapy | CAS 8600001671 | IMMUNOGLOBULIN HUMAN NORMAL IFAS |
| Intravenous immunoglobulin therapy | RECNO 900708 | OTHER IMMUNOGLOBULINS |
| Intravenous immunoglobulin therapy | RECNO 900722 | IMMUNE SERA AND IMMUNOGLOBULINS |
| Intravenous immunoglobulin therapy | RECNO 900728 | IMMUNOGLOBULINS |
| Intravenous immunoglobulin therapy | RECNO 900914 | SPECIFIC IMMUNOGLOBULINS |
| Intravenous immunoglobulin therapy | RECNO 901112 | IMMUNOGLOBULINS, NORMAL HUMAN |

Abbreviations: CAS : Chemical Abstract Service Registry Number RECNO : Drug Record Number

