### **8.3 ADVERSE EVENTS AND SERIOUS ADVERSE EVENTS**

#### **Adverse event of special interest**

An adverse event of special interest (AESI) is an AE (serious or nonserious) of scientific and medical concern specific to the Sponsor's product or program, for which ongoing monitoring and immediate notification by the Investigator to the Sponsor is required. Such events may require further investigation in order to characterize and understand them. Adverse events of special interest may be added, modified or removed during a study by protocol amendment.

For these AESIs, the Sponsor will be informed immediately (ie, within 24 hours), per SAE notification described in [Section 10.3](#), even if not fulfilling a seriousness criterion, using the corresponding pages in the CRF (to be sent) or screens in the e-CRF.

- Anaphylactic reactions
- Systemic hypersensitivity reactions
- Helminthic infections
- Any severe type of conjunctivitis or blepharitis
- Keratitis
- Clinically symptomatic eosinophilia (or eosinophilia associated with clinical symptoms)
- Significant ALT elevation
  - ALT  $>5 \times$  the ULN in participants with baseline ALT  $\leq 2 \times$  ULN;  
or
  - ALT  $>8 \times$  ULN if baseline ALT  $>2 \times$  ULN.
- Pregnancy of a female subject entered in a study as well as pregnancy occurring in a female partner of a male subject entered in a study with IMP/non-investigational medicinal product (NIMP)
  - Pregnancy occurring in a female participant entered in the clinical trial or in a female partner of a male participant entered in the clinical trial. It will be qualified as an SAE only if it fulfills 1 of the seriousness criteria
  - In the event of pregnancy in a female participant, IMP should be discontinued.
  - Follow-up of the pregnancy in a female participant or in a female partner of a male participant is mandatory until the outcome has been determined.
  - Abnormal pregnancy outcomes (eg, spontaneous abortion, fetal death, stillbirth, congenital anomalies, ectopic pregnancy) are considered SAEs.

- Symptomatic overdose (serious or nonserious) with IMP/NIMP
  - An overdose (accidental or intentional) with the IMP is an event suspected by the Investigator or spontaneously notified by the participant and defined as at least twice the intended dose during an interval of less than 11 days. The circumstances (ie, accidental or intentional) should be clearly specified in the overdose form.

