5.6 APPENDIX 6 SELECTION CRITERIA FOR AE/MEDICATION GROUPINGS

Table 15 - List of PTs or Medications for CMQs/CDGs

| Grouping | Preferred Term/ Medication Code | Preferred Term/ Medication |
|------------------------------------|------------------------------------|--|
| Conjunctivitis | 10001257 | Adenoviral conjunctivitis |
| Conjunctivitis | 10010725 | Conjunctival irritation |
| Conjunctivitis | 10010726 | Conjunctival oedema |
| Conjunctivitis | 10010736 | Conjunctival ulcer |
| Conjunctivitis | 10010741 | Conjunctivitis |
| Conjunctivitis | 10010744 | Conjunctivitis allergic |
| Conjunctivitis | 10010745 | Conjunctivitis chlamydial |
| Conjunctivitis | 10010749 | Conjunctivitis gonococcal neonatal |
| Conjunctivitis | 10010754 | Conjunctivitis tuberculous |
| Conjunctivitis | 10010755 | Conjunctivitis viral |
| Conjunctivitis | 10018258 | Giant papillary conjunctivitis |
| Conjunctivitis | 10021629 | Inclusion conjunctivitis |
| Conjunctivitis | 10030861 | Ophthalmia neonatorum |
| Conjunctivitis | 10048908 | Seasonal allergy |
| Conjunctivitis | 10049458 | Herpes simplex virus conjunctivitis neonatal |
| Conjunctivitis | 10051625 | Conjunctival hyperaemia |
| Conjunctivitis | 10053991 | Inclusion conjunctivitis neonatal |
| Conjunctivitis | 10061784 | Conjunctivitis bacterial |
| Conjunctivitis | 10062889 | Pingueculitis |
| Conjunctivitis | 10063669 | Photoelectric conjunctivitis |
| Conjunctivitis | 10067317 | Oculorespiratory syndrome |
| Conjunctivitis | 10067817 | Acute haemorrhagic conjunctivitis |
| Conjunctivitis | 10069166 | Blebitis |
| Conjunctivitis | 10071570 | Ligneous conjunctivitis |
| Conjunctivitis | 10074701 | Noninfective conjunctivitis |
| Conjunctivitis | 10075264 | Oculoglandular syndrome |
| Conjunctivitis | 10080825 | Conjunctivitis fungal |
| Conjunctivitis | 10084034 | Conjunctival suffusion |
| Intravenous immunoglobulin therapy | CAS 8000012671 | IMMUNOGLOBULIN HUMAN NORMAL |
| Intravenous immunoglobulin therapy | CAS 8000050682 | IMMUNOGLOBULIN, PORCINE |
| Intravenous immunoglobulin therapy | CAS 8000056919 | IMMUNOGLOBULIN G HUMAN |
| Intravenous immunoglobulin therapy | CAS 8600000563 | IMMUNOGLOBULINS NOS |
| Intravenous immunoglobulin therapy | CAS 8600001670 | IMMUNOGLOBULIN HUMAN NORMAL SLRA |
| Intravenous immunoglobulin therapy | CAS 8600001671 | IMMUNOGLOBULIN HUMAN NORMAL IFAS |
| Intravenous immunoglobulin therapy | RECNO 900708 | OTHER IMMUNOGLOBULINS |

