Risk differences (constructed using the Miettinen and Nurminen method) and hazard ratios (Cox proportional hazards model) for dupilumab versus placebo with corresponding 95% CIs will be provided for the overview table, and common TEAEs (PT $\geq 2\%$ in any intervention group).

Participants without an event will be censored at the end of the treatment-emergent period in the Cox model. Forest plots will also be presented.

Analysis of deaths

In addition to the analyses of deaths included in [Table 5](#) the number (%) of participants in the following categories will be provided:

- Deaths during the treatment-emergent and post-treatment periods
- Deaths in non-randomized or randomized but not treated participants

Analysis of adverse events of special interest (AESIs) and other AEs of interest

Adverse events of special interest (AESIs) and other AEs of interest will be selected for analyses as indicated in [Table 7](#). Number (%) of participants experiencing at least one event will be provided for each event of interest. Tables will be sorted as indicated in [Table 5](#).

Table 7 - Selections for AESIs and other AEs of interest

| AE Grouping | Criteria |
|---|--|
| AESI | |
| Anaphylactic reaction | Anaphylactic reaction algorithmic approach (Introductory Guide for Standardised MedDRA Queries (SMQs) Version 18.1): includes anaphylactic reaction narrow SMQ (20000021) terms and programmatic identification of cases based on occurrence of at least two preferred terms meeting the algorithm criteria occurring within 24 hours of each other. The latter cases identified using the algorithm will undergo blinded medical review taking into account the timing of events relative to each other and to IMP administration for final determination of an anaphylactic reaction or not. |
| Systemic hypersensitivity reactions | SMQ [20000214] hypersensitivity narrow search and [AE corrective treatment/therapy = 'Y' or Action taken with IMP = 'Drug withdrawn' or Action taken with IMP = 'Drug interrupted'] followed by blinded medical review (documented process) for selection of relevant systemic hypersensitivity events. |
| Helminthic infections | CMQ10544 based on HLT as "Helminthic disorder". |
| Any severe type of conjunctivitis | CMQ10498 based on PTs (See Section 5.6 ^a) and "Severe" ticked in Adverse Events eCRF page. |

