| Any severe type of blepharitis | CMQ10497 based on HLT as "Lid, lash and lacrimal infections, irritations and inflammations" and "Severe" ticked in Adverse Events eCRF page. |
| Keratitis | CMQ10642 based on the following PTs [keratitis, allergic keratitis, ulcerative keratitis, atopic keratoconjunctivitis, herpes ophthalmic, ophthalmic herpes simplex, corneal infection] ^a . |
| Clinically symptomatic eosinophilia (or eosinophilia associated with clinical symptoms) ^b | CMQ10641 (based on HLT = Eosinophilic disorders or PT = Eosinophil count increased) and AESI is "Yes". |
| Pregnancy of a female patients entered in a study as well as pregnancy occurring in a female partner of a male patient entered in a study with IMP/NIMP | "Pregnancy" or "Partner Pregnancy" checked on the Pregnancy eCRF page as reported by the investigator. |

| AE Grouping | Criteria |
|--|---|
| Significant ALT elevation | ALT >5 × ULN in participants with baseline ALT ≤2 × ULN; OR ALT >8 × ULN if baseline ALT >2 × ULN. |
| Symptomatic overdose with IMP | Symptomatic Overdose is answered Yes, with Overdose of IMP answered Yes on AE eCRF.. |
| Symptomatic overdose with NIMP | Symptomatic Overdose is answered Yes, with Overdose of NIMP answered Yes on AE eCRF.. |
| Other selected AE Grouping | |
| Serious injection site reactions or severe injection site reactions that last longer than 24 hours | HLT = 'Injection site reactions' and either with serious status, or with severe status and (AE end date/time - AE start date/time) ≥24 hours or ongoing. |
| Severe or serious infection | Primary SOC = 'Infections and infestations' and with severe or serious status. |
| Drug-related hepatic disorder | SMQ [20000006] Drug-related hepatic disorders- narrow. |
| Injection site reaction | HLT = 'Injection site reactions'. |
| Malignancy | SMQ [20000091]- Malignant or unspecified tumors narrow. |
| Conjunctivitis (narrow) | CMQ10644 based on the following PTs [Conjunctivitis, Conjunctivitis allergic, Conjunctivitis bacterial, Conjunctivitis viral, Atopic keratoconjunctivitis] ^a . |
| Conjunctivitis (broad) | CMQ10645 based on the following PTs [Conjunctivitis, Conjunctivitis allergic, Conjunctivitis bacterial, Conjunctivitis viral, Atopic keratoconjunctivitis, Blepharitis, Dry eye, Eye irritation, Eye pruritus, Lacrimation increased, Eye discharge, Foreign body sensation in eyes, Photophobia, Xerophthalmia, Ocular hyperaemia, Conjunctival hyperaemia] ^a . |

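### Study C SAP: the severe-conjunctivitis AESI list includes Seasonal allergy without explanation and leaves out Atopic keratoconjunctivitis, so its row can count an event with no eye finding

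*SAP*

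**What the plan says.** Protocol section 8.3 names "Any severe type of conjunctivitis or blepharitis" as an adverse event of special interest and lists keratitis as a separate one.

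The Study C SAP (section 4.7.2, Table 7) selects the conjunctivitis part by "CMQ10498 based on PTs (See Section 5.6 ^a", combined with the severe box on the adverse event page. The terms are in Appendix 6, Table 13. They include "10048908 | Seasonal allergy", and there is no row for Atopic keratoconjunctivitis. The Study A and Study B SAPs print the same terms.

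Table 7 also defines three conjunctivitis groupings that have no severity condition. The narrow one is "CMQ10644 based on the following PTs [Conjunctivitis, Conjunctivitis allergic, Conjunctivitis bacterial, Conjunctivitis viral, Atopic keratoconjunctivitis". The broad one has 16 terms, among them "Conjunctivitis viral, Atopic keratoconjunctivitis, Blepharitis, Dry eye, Eye irritation, Eye pruritus, Lacrimation increased". The FDA one has seven. None contains Seasonal allergy; the narrow and broad ones contain Atopic keratoconjunctivitis, and the FDA one does not. The Keratitis AESI (CMQ10642) also contains Atopic keratoconjunctivitis, at any severity.

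Footnote a to Table 7 allows the lists to be adjusted, but only for MedDRA version changes.

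**The concern.** Protocol section 2.3 lists conjunctivitis among the identified adverse drug reactions of dupilumab, so the severe-conjunctivitis row will be read as a measure of a known risk. A row of that name should contain eye events. Seasonal allergy does not name one, and the SAP gives no reason for including it. Allergic rhinitis is one of the comorbidities the Study C SAP collects (section 5.3), so allergy events are plausible in this population, although the documents give no rate for severe ones.

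The second issue is one of classification. Atopic keratoconjunctivitis is conjunctivitis in two of the SAP's groupings but not in the row meant to cover any severe type of it. A reader who sets the severe line of the narrow grouping beside this AESI may find a participant in the first who is missing from the second, with nothing in the SAP to explain why.

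**Working it through.** The plan states no figure to reproduce. The check compares the printed term lists and then follows two hypothetical events through the rules.

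**1. Lists side by side** (Study C SAP, Table 13 against Table 7)

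| Grouping | Terms | Also in the severe list | Seasonal allergy | Atopic keratoconjunctivitis |
|---|---|---|---|---|
| Severe conjunctivitis AESI (CMQ10498) | 28 | – | yes | no |
| Conjunctivitis (narrow) | 5 | 4 | no | yes |
| Conjunctivitis (broad) | 16 | 5 | no | yes |
| Conjunctivitis (FDA) | 7 | 5 | no | no |
| Keratitis AESI (CMQ10642) | 7 | 0 | no | yes |

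Atopic keratoconjunctivitis is the only narrow term missing from the severe list. Six severe-list terms appear in at least one of the three conjunctivitis groupings: the four shared narrow terms, Conjunctival hyperaemia (broad) and Giant papillary conjunctivitis (FDA). The remaining 28 − 6 = 22, Seasonal allergy among them, appear in none.

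**2. A severe Seasonal allergy event with no eye finding.** It meets both conditions, the listed term and the severe tick. Nothing later removes it. In the same table, algorithm-identified anaphylaxis cases and the hypersensitivity search results go to blinded medical review; this row has no such step. The event enters the row's incidence, risk difference and hazard ratio. It also enters the overview row for any treatment-emergent AESI, which has its own risk difference and hazard ratio, unless the participant is already counted there for another AESI.

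**3. A severe Atopic keratoconjunctivitis event.** It is not in the severe-conjunctivitis row. It is in the Keratitis AESI, so the any-AESI row still counts the participant. It is also in the narrow and broad groupings. Section 4.7.2 calls for counts by maximum intensity for each AESI and other selected grouping, so the event shows on the severe line of the narrow grouping. That line can therefore exceed the severe-conjunctivitis row.

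**4. Size of one event.** Protocol section 9.2 plans 75 participants per arm in Study C: 1/75 = 0.0133, or 1.3% of an arm.

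**The case against.** The strongest reply is that these are separate definitions that were never meant to agree. The AESI is limited to severe events and the groupings are not; 22 of its 28 terms are in none of the three; the groupings differ among themselves; and nothing in the SAP requires one to nest in another. This stands. A reader might infer that the counts must disagree because of the two terms, but the documents support only that they can, and only if such a severe event occurs.

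A reader might also infer that severe Atopic keratoconjunctivitis is lost as an AESI. It is not: the Keratitis AESI captures it. Filing a term that is both keratitis and conjunctivitis under keratitis is defensible, which is why a footnote would be enough.

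Section 4.7.2 already gives AESI counts by query and preferred term, and summarizes investigator-reported AESIs separately. A Seasonal allergy event would thus be visible as its own line. This removes much of the force, but not all: the row's risk difference and hazard ratio, and the any-AESI overview row, are not split by term.

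The list is shared with Studies A and B, and changing it for Study C alone weakens like-for-like comparison. This is a fair cost, and showing the row both ways meets it. Study C already departs from the other two SAPs on another AESI: its selection for symptomatic eosinophilia adds a requirement that the AESI flag be yes.

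Finally, Study C prints "1001257 | Adenoviral conjunctivitis" where Studies A and B print "10001257 | Adenoviral conjunctivitis". One might infer that a code-based search would miss the event. The documents do not support that: selection is described as based on preferred terms, nothing says the printed codes drive the program, and the missing digit may be a typing or PDF-reading slip. It warrants a check of the printed code and nothing more.

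**Conclusion.** The point holds as a minor one. Under the stated rule, a severe allergy event with no eye finding would be reported as severe conjunctivitis, and the SAP offers neither a reason nor a review step to prevent it. The omission of Atopic keratoconjunctivitis is an unexplained inconsistency with the narrow and broad groupings only, and it leaves the overall AESI count intact.

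The effect is limited to descriptive safety output; section 4.7 plans no safety testing, and no efficacy or type I error result is touched. One misfiled event would add 1.3 percentage points to an arm of 75, which is noticeable if severe events are few. That they will be few is an assumption, since the documents give no expected rate for severe conjunctivitis or severe seasonal allergy. The conclusion also assumes that the printed list is the one applied. The reasons behind the CMQ's terms are not in these documents, so the inclusion is best called unexplained rather than shown to be a mistake.

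**What to change.** Before the Study C database lock:

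- Remove Seasonal allergy from the severe-conjunctivitis AESI. Alternatively, keep it and report the row's incidence, risk difference and hazard ratio with and without it.
- Add Atopic keratoconjunctivitis to the list, or footnote the row to say that it is counted under Keratitis.
- Check the printed code for Adenoviral conjunctivitis against the Study A and B SAPs.

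The cost is a table edit and, if the second display is chosen, one extra row. Removing or adding a term makes the Study C row differ from Studies A and B unless those are re-run. The with-and-without display and the footnote avoid that.
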